#### 2.1 Primary Objectives

1. To explore the link between liver enzymes, NAFLD, obesity and colorectal neoplasia in terms of adenoma burden, site and histological features

2. To assess whether the presence of liver fibrosis, measured using the FIB4 score, affects the risk of colorectal neoplasia

3. To identify which demographics contribute to increased predisposition to colorectal neoplasia

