#### 3.1 Patient Recruitment

Eight Northern Regional Endoscopy Group (NREG- with a strong track record in delivering large endoscopy trials) units and Kettering General Hospital NHS Trust will recruit patients. Sites from NREG include: South Tyneside District Hospital, Freeman Hospital, Northumbria NHS Trust, Sunderland Royal Hospital, James Cook University Hospital, County Durham and Darlington Foundation Trust, Leeds Teaching Hospitals NHS Trust and North Tees University Hospitals.

Approximately 1430 patients undergoing colonoscopy as part of the BCSP or symptomatic service (most commonly patients with iron deficiency anaemia, altered bowel habit, weight loss and rectal bleeding) will be identified from endoscopy lists and recruited by a member of the research team. The final target number of participants will be refined after the first 100 participants have been recruited however this is not expected to vary significantly. Methodology by Peduzzi et al is used to calculate the minimum number of cases required to measure all variables and develop the risk model. Sample size N=10\*(k/p), where k is the number of covariates to be investigated in the model (n=15) and p the smallest of the proportions of positive or negative cases (=ADR=0.15). For non-BCSP population, ADR is around 15%; 1000 from this population are required. Minimum ADR within the BCSP is 35%; 430 cases are required to adequately power and build the model. This will allow resolution of small scale effects of covariates on risk prediction. Using Demidenko's method, the sample size needed for logistic regression with 80% power and 5% level of significance is N=8V/β2, where  $\beta$  is the natural log of the

odds ratio and V is logistic model variance due to covariates. This formula can be rearranged to determine the minimum odds ratio that can be detected at a sample size of 2000 with sufficient power. Assuming a moderate standard error in the regression (se=0.125), and calculating V from the standard error (V=(se\*vN)2) the study will have sufficient statistical power to detect an effect with a small effect size with an odds ratio of 1.42. The final sample size will be refined using data from the first 100 participants and observed effect size(s), however, the total number of recruits will not exceed 2000.

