#### 6. Statistics and Data Analysis

Data from the CRFs will be transferred to a secure and encrypted electronic computer database. Statistical analysis will be undertaken by [name], Professor of Biological Modelling at Newcastle University.

The relationship between adenoma incidence, NAFLD and blood markers will be investigated using logistic regression whilst adjusting for patient-related demographic variables including age and gender. This will assess the independent contribution of predictors to the odds of adenomas being found. Stepwise removal of non-significant covariates will then be used to identify variables best able to predict adenoma presence. ROC plot and AUC analyses of sensitivity and specificity will be used to characterise the ability of the model to discriminate between patients with and without adenomas and their potential as a predictive tool. These analyses assess the independent contribution of variables to the probability that adenomas will be found, but do not allow for confounding, interaction and associated indirect effects on detection. Structural Equation Modelling (SEM) will be used to investigate impact of indirect and direct effects of the predictors on adenoma incidence. Parsimonious models for logistic regression and SEM will be compared in terms of their ability to predict adenoma presence.

As multiple adenomas may occur, the extent to which adenoma number is related to abnormal liver enzymes using Poisson regression models and SEM will be measured, following the same analytical framework. It is anticipated that the presence of multiple adenomas will be zero-inflated, with some patients having zero and others many. The extent to which zero-inflated models (eg allowing for aggregation) improve the prediction of adenomas will be assessed. Robustness and validation of all models will be validated using bootstrapping. The best model will be developed into a predictive tool.

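### The final risk model is reached by dropping non-significant terms, with the liver, fibrosis and obesity exposures unprotected and no statement that the earlier adjusted model answers the objectives

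*Protocol*

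**What the plan says.** Section 6 of the protocol sets out two steps. The first is a logistic regression of adenoma presence on NAFLD and blood markers, adjusted for demographic variables that include age and gender. Of this step it says: "This will assess the independent contribution of predictors to the odds of adenomas being found". The second step is pruning: "Stepwise removal of non-significant covariates will then be used to identify variables best able to predict adenoma presence". The adenoma-count models follow the same framework, the logistic and structural equation models are compared, and the best model becomes the tool. The stated safeguard is: "Robustness and validation of all models will be validated using bootstrapping".

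Section 2.1 lists the exposures as primary objectives. Objective 1 covers liver enzymes, NAFLD and obesity. Objective 2 is: "To assess whether the presence of liver fibrosis, measured using the FIB4 score, affects the risk of colorectal neoplasia". Section 3 names the risk model, with emphasis on obesity-related factors, as the primary outcome, and says the association questions support it.

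Section 3.1 sizes the study with one count for all model terms, "where k is the number of covariates to be investigated in the model (n=15", so the exposures fall under the same word, covariates, that Section 6 uses for the terms to be removed.

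**The concern.** A significance filter suits neither purpose well. For the association objectives, an exposure that misses the threshold disappears from the final model, and no estimate or interval for it is left there. An exposure that survives has been selected for being large in that sample, so its odds ratio is too high on average.

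The exposures also overlap by construction. Section 3.5 defines NAFLD from ALT plus overweight or obesity, and FIB-4 from age, AST, platelets and ALT. Which of them survives is therefore partly chance.

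For the tool, bootstrapping measures optimism fairly only if each resample repeats the removal. Section 3.1 expects the sample size to resolve small covariate effects, and that is the range in which this rule distorts most.

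**Working it through.** **Reproducing the plan's figures (Section 3.1)**

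- Events-per-variable rule, N = 10k/p with k = 15. For "For non-BCSP population, ADR is around 15%; 1000 from this population are required": 10×15/0.15 = 1000. For "Minimum ADR within the BCSP is 35%; 430 cases are required to adequately power and build the model": 10×15/0.35 = 428.6. The sum is 1428.6, which matches the planned total of about 1430.
- Detectable effect: V = (0.125×√2000)² = 31.25, and OR = exp(√(8×31.25/2000)) = exp(0.3536) = 1.424. This matches the stated 1.42.

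**Effect of the filter (normal approximation)**

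Inputs from the protocol are se = 0.125 in the N=2000 calculation and a true OR of 1.42, so b = ln 1.42 = 0.351. I make two assumptions:

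- Removal is at two-sided p>0.05, because no threshold is stated.
- The standard error scales with 1/√N, giving 0.125×√(2000/1430) = 0.148 at N=1430.

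With a₁ = 1.96 − b/se and a₂ = −1.96 − b/se:

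- P(kept) = 1 − Φ(a₁) + Φ(a₂)
- Mean of the kept estimate = b + se×[φ(a₁) − φ(a₂)]/P(kept)

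At N=2000, b/se = 2.81 and a₁ = −0.85, so P(kept) = 0.801. The mean kept log-OR is 0.394, which is OR 1.48, and 0.394/0.351 = 1.12. At N=1430, b/se = 2.37 and a₁ = −0.41, so P(kept) = 0.660. The mean kept log-OR is 0.433, which is OR 1.54, and 0.433/0.351 = 1.23.

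| True OR | N | Removed | Mean OR when kept | Kept log-OR ÷ true |
|---|---|---|---|---|
| 1.2 | 2000 | 69% | 1.38 | 1.78 |
| 1.2 | 1430 | 77% | 1.45 | 2.05 |
| 1.42 | 2000 | 20% | 1.48 | 1.12 |
| 1.42 | 1430 | 34% | 1.54 | 1.23 |
| 2.0 | 2000 | <1% | 2.00 | 1.00 |
| 2.0 | 1430 | <1% | 2.00 | 1.00 |

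**Simulation of backward elimination**

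This used 15 covariates, the planned recruitment mix at adenoma rates of 35% and 15%, and 600 runs per setting. Assumptions from outside the protocol are an exposure prevalence of 30%, a correlation of 0 or 0.6 among five exposure-related covariates, and three other non-null covariates besides recruitment route. The true OR was 1.42.

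| N | Correlation | Removed | Mean OR when kept | Mean OR, full model |
|---|---|---|---|---|
| 1430 | 0 | 32% | 1.52 | 1.42 |
| 1430 | 0.6 | 40% | 1.62 | 1.42 |
| 2000 | 0 | 18% | 1.48 | 1.43 |
| 2000 | 0.6 | 24% | 1.54 | 1.44 |

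The simulation agrees with the approximation, and overlap between the exposures makes matters worse. The full model, read whatever its p-value, shows no material bias.

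**Bootstrap**

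In a further 15-candidate simulation with assumed effects, the true AUC optimism after backward removal was 0.012. Bootstrapping only the final model found about 0.005. Repeating the removal in each resample found 0.013.

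**The case against.** The strongest reply is that Section 6 fits an adjusted model before anything is removed and ties removal to prediction. A reader might infer that the study loses its answer on liver disease and obesity altogether. The documents do not support that, because the first-step estimates are unselected and would be sound if reported. What remains is that the protocol does not name that model as the answer to Objectives 1–3, its description of the first step does not name FIB-4 or obesity, and it carries the pruned model forward. Nor does the text say that age and gender may be dropped. It lists them as adjustment variables and leaves their status in the second step open.

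A reader might also blame the removals wholly on the stepwise rule. Most of it is limited power, which the full model shares: in a 15-candidate simulation with assumed effects, the exposure was kept in 42% of runs and was significant in the full model in 35%. The difference is that the full model still gives an estimate and interval when p is large.

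A third tempting reading is that stepwise removal itself makes predicted risks too extreme. It does not: the unpenalised full model had the worse calibration slope (0.92 against 0.95). Nor are intervals generally too narrow. At OR 1.42 and N=1430, coverage among kept estimates is about 96%. It falls to about 89% at OR 1.2.

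Finally, the threshold and the bootstrap details may properly sit in an analysis plan that is not shown. Their absence is not counted here. The point rests on the removal rule that the protocol states.

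**Conclusion.** The point holds in limited form. The protocol fixes significance-based removal as the route to its primary outcome, protects none of the exposures that form its primary objectives, and does not assign those objectives to the unselected model. At its own detectable effect, a real exposure is dropped in about one study in five at N=2000 and one in three at N=1430, and the surviving log odds ratio averages 12% or 23% too large.

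These sizes rest on removal at p>0.05, on the protocol's standard error of 0.125, and on rescaling it to N=1430. If 0.125 were meant to apply at N=1430 as well, the N=2000 figures would hold there. A laxer threshold would reduce both effects. A rarer exposure, such as FIB-4 above 2.67, would have a larger standard error and suffer more. The overstatement is an average over retained estimates near the detection limit, not a property of every result. The planned bootstrapping does not by itself remove bias in retained odds ratios.

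**What to change.** State in Section 6 that the associations for Objectives 1–3, including FIB-4, NAFLD, liver enzymes and BMI, are reported with confidence intervals from the pre-specified adjusted model before any removal, whatever their p-value.

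For the prediction tool, choose one of two routes:

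- Use penalised regression.
- Keep backward removal, but repeat both the removal and the choice between model types in every bootstrap resample, and shrink the final coefficients by the bootstrap calibration slope.

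The change affects wording and code only and needs no extra patients. The downside is slightly more analysis work and slightly less favourable apparent performance.

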Approximately 400,000 colonoscopies are performed each year within the NHS for the investigation of gastrointestinal symptoms, including altered bowel habit, rectal bleeding and iron deficiency anaemia. Adenoma detection rate (ADR), defined as the number of procedures in which at least one adenoma is detected, is a widely accepted quality measure. A recent colonoscopy audit demonstrated an average polyp detection rate of 32.1%; however, ADR is variable between colonoscopists. A recent study estimated mean ADR of 15.9%. Patients found to have adenomas receive surveillance procedures, however these are currently based entirely upon number and size of adenomas with no patient factors considered. The NHS Bowel Cancer Screening Programme (BCSP)

invites all individuals aged 60-74 to undertake biennial faecal occult blood testing (FOBt). Screening is currently population based and non-targeted. Patients with a positive FOBt are invited for colonoscopy. The national Bowelscope screening programme is currently being rolled out in England and Wales, with the Lead applicants unit the first nationally to deliver this programme. All individuals aged 55 are invited for a single flexible sigmoidoscopy and adenoma clearance. Those deemed to be high risk undergo completion colonoscopy.

The mean ADR per colonoscopist within the FOBt BCSP is 46.5%, which is much higher than the symptomatic population due to the targeted nature of the programme. The BCSP has demonstrated a significant stage shift in CRC diagnosed. At present, the FOBt based screening programme is not providing protection against right sided CRC. A trial within the Scottish screening programme demonstrated that screening was an effective environment for interventions to alter patient behaviour.

In summary, although a study in an Asian population suggested an association between NAFLD and colorectal neoplasia, this has not been repeated in a Western population. It is important that the association is explored in a Western population but using non-invasive markers of liver disease and a wider range of colorectal neoplasia risk factors. This will allow development of a model to predict colorectal adenoma risk guiding screening and surveillance.

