#### 2. Study Objectives

To measure the extent to which individuals with obesity and abnormal liver function are at increased risk of developing colorectal adenomas and CRC. This study aims to quantify that risk by developing a model of obesity-related and other known CRC risk factors. In addition the model will be refined using non-invasive measures of liver disease.

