#### 3. Study Design

A multi-centre observational study will identify colorectal neoplasia burden in patients undergoing index screening or diagnostic colonoscopy. Non-invasive markers of liver disease and obesity will be assessed and a multivariate model constructed. The primary outcome is to develop a risk model with emphasis on obesity-related factors, particularly in the population with abnormal liver enzymes, to inform colorectal screening. Secondary outcomes will support this model by identifying demographics which contribute to increased predisposition to colorectal neoplasia, additionally assessing whether the presence/degree of liver fibrosis affects this risk. The link between NAFLD, obesity and colorectal neoplasia in terms of adenoma burden, site and histological features will also be explored.

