#### 3.2 Inclusion criteria

- 1. Aged 18 years and over
- 2. Able to give informed consent
- 3. Indications:
  - a. Patients with positive faecal occult blood test (FOBt) referred for index colonoscopy as part of Bowel Cancer Screening Programme
  - b. Colonoscopy conversion from Bowelscope
  - c. Index diagnostic colonoscopy due to new gastrointestinal symptoms (including but not restricted to diarrhoea, change in bowel habit, abdominal pain, PR bleeding, weight

loss), iron deficiency anaemia, family history of CRC, abnormal findings on cross sectional imaging

Recruitment materials will be produced in English; however, if language difficulties emerge in an interested patient, a professional translation service specialising in facilitating phone consultations will be used.

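### Section 6 prunes predictors stepwise and names only ROC/AUC, with no comparison of the model with and without liver measures, so the refinement promised in section 2 is not measured

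*Protocol*

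**What the plan says.** Protocol section 2 describes a model built from obesity and established risk factors, and then a second step: "In addition the model will be refined using non-invasive measures of liver disease". Section 3 gives this model first rank: "The primary outcome is to develop a risk model with emphasis on obesity-related factors, particularly in the population with abnormal liver enzymes". Its intended use is in screening.

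Section 6 sets out the analysis of adenoma presence in this order:

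- Logistic regression of adenoma on NAFLD and blood markers, adjusted for demographics including age and gender. "This will assess the independent contribution of predictors to the odds of adenomas being found".
- Selection: "Stepwise removal of non-significant covariates will then be used to identify variables best able to predict adenoma presence".
- Performance: "ROC plot and AUC analyses of sensitivity and specificity will be used to characterise the ability of the model to discriminate".
- Structural equation modelling (SEM) for direct and indirect effects, then: "Parsimonious models for logistic regression and SEM will be compared in terms of their ability to predict adenoma presence".
- Bootstrap validation of all models. The quantity to be validated is not named. The best model then becomes the tool.

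For adenoma number, section 6 also asks whether zero-inflated models predict better.

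The population is broad. Section 3.2 admits patients "Aged 18 years and over", from both the screening programme and the symptomatic service. According to section 1, the screening programme "invites all individuals aged 60-74 to undertake biennial faecal occult blood testing", and Bowelscope invites people at 55.

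**The concern.** Section 2 asks an incremental question: how much better is adenoma predicted once liver measures join the known risk factors? Section 6 answers a different one: which covariates survive pruning, and how well does the surviving model discriminate? The AUC of a selected model does not say which of its predictors earned it. Age and referral route are both likely to separate patients with adenomas from those without, so the figure could be respectable whether or not the liver measures help.

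At stake is the main product of the study. Liver tests could be put into a screening tool, or left out of it, without anyone having measured what they add to prediction. AUC also says nothing about whether predicted risks are numerically right, and that matters once a model is turned into a tool.

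**Working it through.** **1. The plan's own figures reproduce.** With N = 10k/p and k = 15 (section 3.1), 10 × 15/0.15 = 1000 symptomatic patients and 10 × 15/0.35 = 428.6, stated as 430, screening patients. With N = 8V/β² and V = (se × √N)², β = √8 × 0.125 = 0.354 and the odds ratio (OR) is e^0.354 = 1.42. The sample size is not in dispute here. The protocol gives no AUC target.

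**2. Aim against analysis.** The comparisons named in section 6 are logistic regression against SEM and, for counts, zero-inflated against other models. Both compare types of model. Neither compares sets of predictors.

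**3. The liver variables overlap the base predictors by construction.**

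- FIB-4 has age in its numerator (section 3.5).
- The fatty liver index contains height, weight and waist (section 1).
- The fatty liver definition requires overweight or obesity (section 3.5).

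Stepwise removal among such variables may keep one and drop another that carries much the same information. Survival in the model is therefore not a measure of added liver information. As an illustration, FIB-4 was simulated from AST, ALT and platelets with no relation to adenoma (assumed: AST and ALT log-normal with median 25 and log-SD 0.3 and 0.4; platelets mean 260, SD 60; age as in step 5). It still gave an AUC of 0.54, 0.57 and 0.59 for age ORs of 1.3, 1.5 and 1.8 per decade, through its age term alone.

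**4. AUC from referral pathway alone, using document figures only.** For a binary predictor, AUC = 0.5 + (TPR − FPR)/2. Here TPR is the screening share of patients with adenoma, and FPR is the screening share of patients without.

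- Screening rate 35% (section 3.1): patients with adenoma 430 × 0.35 = 150.5 and 1000 × 0.15 = 150; without, 279.5 and 850. TPR = 150.5/300.5 = 0.501, FPR = 279.5/1129.5 = 0.247, AUC = **0.627**.
- Screening rate 46.5% (section 1): with adenoma 199.95 and 150; without, 230.05 and 850. TPR = 199.95/349.95 = 0.571, FPR = 230.05/1080.05 = 0.213, AUC = **0.679**.

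These apply if the two groups are pooled and the model contains pathway. A variable that stands in for pathway, such as age, would carry part of the effect.

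**5. AUC from age, with assumed inputs.** The protocol gives neither an age distribution nor an age effect. Assumed: mean 60, SD 14, limited to 18–90, and adenoma rate 21% (300.5/1430). The marker is independent of age, with OR 1.42 per SD.

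| Age OR per decade | Age alone, 18+ | Gain from marker, 18+ | Age alone, 60–74 | Gain from marker, 60–74 |
|---|---|---|---|---|
| 1.3 | 0.60 | 0.039 | 0.53 | 0.071 |
| 1.5 | 0.64 | 0.028 | 0.55 | 0.061 |
| 1.8 | 0.70 | 0.020 | 0.57 | 0.050 |

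A binary marker with OR 1.42 and 10% or 30% prevalence gains 0.002 to 0.010 over ages 18+.

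**6. What the planned regression can show.** With age OR 1.5, N = 1430 and 400 simulated studies, a likelihood-ratio test of one standardised marker adjusted for age has power of about 100% for OR 1.42 and 74% for OR 1.2 (92% at N = 2000). The mean gain in AUC at N = 1430 is 0.029 and 0.009. Association and predictive gain are different quantities: a marker can be detected reliably and still add little discrimination.

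**7. Calibration.** AUC depends only on the ranking of risks. In a simulated example, shifting the predictions so that their mean rose from 15% to 33% left AUC at exactly 0.675.

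**The case against.** The best defence is that AUC is not the test of the liver markers. Section 6 first estimates their adjusted association with adenoma, adds SEM for direct and indirect effects, and relates adenoma number to liver enzymes. Adjusted odds ratios do answer how far obesity and abnormal liver function raise risk. This stands. A reader might infer that the plan cannot show any liver contribution, and step 6 contradicts that.

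Three further objections have force.

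- Section 6 does not say that one AUC will be computed over everyone, and section 3.1 sizes the two pathways separately. The pooling argument is therefore conditional.
- A reader might infer that age will drive the AUC. The protocol has no figures to establish this, and step 5 rests on assumed ones. The wide age range also belongs to the population under study.
- A reader might infer that a liver marker's gain would be too small to see in an AUC. That fits a single binary marker. Many of the liver measures are continuous, and for those the gain could be 0.02 to 0.04.

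It can also be said that calibration and subgroup AUCs belong in a statistical analysis plan, which is not shown. For calibration alone that is fair. It does not dispose of the main point, because the protocol itself states the refinement aim and itself fixes a sequence of analyses and comparisons that does not deliver it.

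**Conclusion.** The point holds in a bounded form and should be acted on. Section 2 promises refinement by liver measures, and section 6 measures association and final-model discrimination but not added predictive value. Stepwise selection among overlapping variables does not supply the missing quantity. This conclusion follows from the text and needs no assumption.

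The size of the possible misreading is conditional. If the pathways are pooled, the protocol's own rates put AUC at 0.627 to 0.679 with no liver information. The age figures (about 0.60 to 0.70 over 18+, 0.53 to 0.57 within 60–74) depend on the assumed age distribution and effects, and only illustrate how case mix can raise an overall AUC. Nothing here shows that liver measures lack value, or that the study is too small to find it.

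**What to change.** In section 6, prespecify two nested logistic models:

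- **Base:** the known risk factors, including age, sex, family history, smoking and an obesity measure, together with referral pathway.
- **Extended:** the same model plus one prespecified block of liver measures, kept whole.

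Fit both on the same patients. This needs stating, because section 3.5 keeps patients with haemolysed liver samples in the study. Then report:

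- the likelihood-ratio test for the liver block;
- the change in AUC with a confidence interval, corrected for optimism by the bootstrap already planned;
- AUC within each referral pathway and within the screening-age band;
- the bootstrap calibration intercept and slope, before the model is made into a tool.

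Stepwise selection and SEM can remain as further analyses. No new data are needed. The cost is slightly more analysis, and the AUC within pathway or screening ages will probably be lower than a pooled figure.

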#### 3.5 Data Collection

On attendance for colonoscopy and following completion of a written consent form, the participant will be asked to complete a health questionnaire. This can be done either by the participant alone or with help from a member of the research team. This questionnaire will include the following details:

- 1. Age
- 2. Ethnicity
- 3. Gender

- 4. Smoking History- current and previous
- 5. Alcohol consumption- current and previous
- 6. Medication history
- 7. Family history of colorectal cancer
- 8. Family history of ischaemic heart disease
- 9. History of liver disease
- 10. Hypertension history
- 11. Diabetic history
- 12. History of chronic kidney disease (stage 4/5, eGFR <30ml/min)
- 13. History of atrial fibrillation
- 14. History of rheumatoid arthritis
- 15. Previous anti-obesity surgery

The clinical notes will be used to confirm the indication for the colonoscopy and to support the health questionnaire where participants are unsure of details. The research nurse will measure blood pressure, weight, height, waist circumference and calculate the body mass index (BMI in kg/m^2). This information, including the health questionnaire, will be entered onto the case report form (CRF).

Blood tests will be taken to identify patients with fatty liver defined as:

- Definite if patients have raised ALT levels (above the upper limit of normal) and are overweight or obese (in the absence of excessive alcohol consumption)
- Probable if the ALT >30 IU/ml for males and >19 IU/ml for females and they are overweight or obese (in the absence of excessive alcohol consumption)

We will also determine stage of fibrosis defined by FIB-4 score ((age x AST)/(platelets x (VALT)) as:

- No / mild: FIB-4 score <1.3
- Moderate: FIB-4 score 1.3 2.67
- Advanced: FIB-4 score >2.67

We will also determine the patient's Qrisk 2 score and Fatty Liver Index (FLI) Score.

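### Fibrosis is given only as three FIB-4 bands, and the adenoma-count exposure is worded as abnormal liver enzymes; modelling these measured values as numbers would lose less information at almost no cost

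*Protocol*

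**What the plan says.** Two places in the Protocol word a liver exposure as a class.

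- Section 3.5, fibrosis: "We will also determine stage of fibrosis defined by FIB-4 score", followed by three bands: below 1.3, 1.3 to 2.67, and above 2.67. No other form of the fibrosis exposure is given. Primary objective 2 (section 2.1) is "To assess whether the presence of liver fibrosis, measured using the FIB4 score, affects the risk of colorectal neoplasia".
- Section 6, count model: the Poisson and structural equation models are to measure "the extent to which adenoma number is related to abnormal liver enzymes". No cut-off or coding is attached to the word abnormal.

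Section 3.5 also defines fatty liver by ALT limits combined with weight and alcohol: "Definite if patients have raised ALT levels (above the upper limit of normal) and are overweight or obese", and "Probable if the ALT >30 IU/ml for males and >19 IU/ml for females and they are overweight or obese".

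Other wording is open. The model for adenoma presence in section 6 reads "The relationship between adenoma incidence, NAFLD and blood markers will be investigated using logistic regression", with no scale. Primary objective 1 names liver enzymes without the word abnormal. Section 3 speaks of the presence or degree of fibrosis, and says of the risk model that its emphasis lies "particularly in the population with abnormal liver enzymes".

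**The concern.** ALT, AST, GGT and the platelet count come from the laboratory as numbers, and FIB-4 is a formula built from age and three of them. Putting such a value into two or three classes treats patients just either side of a limit as different and everyone within a class as alike. It may also leave a small top class to carry the contrast.

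Three things are at stake. The protocol expects small effects (odds ratio 1.42), so lost information matters. Section 3 asks about degree of fibrosis, which three bands describe coarsely. The end product is a predictive tool, and classed predictors would give it artificial steps at the limits. None of the planned models (logistic, Poisson, zero-inflated, structural equation) needs cut enzymes or cut FIB-4.

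**Working it through.** **The protocol's own figures (section 3.1).** With k = 15 covariates, N = 10k/p gives 10 × 15/0.15 = 1000 and 10 × 15/0.35 = 428.6. The sum is 1428.6, against about 1430 stated. The detectable odds ratio from N = 8V/β² with V = (se√N)² and se = 0.125 is exp(√8 × 0.125) = 1.42, as stated. Both reproduce. The protocol states no figure for loss from classing and no share of patients above any limit, so the shares below are assumptions.

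**Two classes.** For a normal exposure with a linear effect, a cut with share q above it keeps φ(z)²/(q(1−q)) of the information, where z is the cut point and φ the normal density.

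| Share above cut | Kept | Lost | 1430 patients work like |
|---|---|---|---|
| 50% | 0.637 | 36% | 910 |
| 20% | 0.490 | 51% | 701 |
| 10% | 0.342 | 66% | 489 |

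The median split is the best case, so 36% is the floor.

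**Logistic check.** The formula holds for small effects. In simulations with N = 1430, an odds ratio of 1.42 per standard deviation, risk at the mean exposure of 0.15 or 0.21, and 300 runs per setting, the loss was 37–38% at a 50% share, 42–43% at 20% and 53–56% at 10%. A direct large-sample calculation of the same Wald tests gives 36–37%, 41–42% and 55–57%. The logistic figures for a 20% or 10% share, about 42 to 57%, are therefore the ones to use. They lie below the formula's 51% and 66%.

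**Power.** A test with 80% power on the number has an expected z of 1.960 + 0.842 = 2.802. After losing a fraction L, power is Φ(2.802√(1−L) − 1.960):

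- L = 0.36: 61%
- L = 0.42: Φ(2.134 − 1.960) = 57%
- L = 0.57: Φ(1.837 − 1.960) = 45%

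**Three FIB-4 bands.** The share kept is Σ pⱼmⱼ², with pⱼ the share and mⱼ the mean standardised value in band j. FIB-4 is assumed log-normal and cut at ln 1.3 and ln 2.67.

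| Median | Geometric SD | Shares, low/middle/high | Kept | Lost |
|---|---|---|---|---|
| 1.0 | 1.5 | 74/25/1% | 0.564 | 44% |
| 1.4 | 1.9 | 45/39/16% | 0.776 | 22% |

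Other assumed splits give 19% (27/46/27), 25% (50/40/10), 31% (60/35/5), 38% (70/25/5) and 48% (80/17/3). About 20 to 45% is a fair summary.

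**FIB-4 and its components.** From the formula in section 3.5, log FIB-4 = log age + log AST − log platelets − ½ log ALT. In an age-adjusted model that also holds log ALT and log AST, what remains of log FIB-4 is mainly the platelet count. Its coefficient would then not answer objective 2.

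**The case against.** The strongest reply is that the protocol nowhere says the exposures enter the models only as classes. The logistic model names blood markers without a cut, objective 1 says liver enzymes, and section 3 allows for degree of fibrosis. Section 3.5 is about data collection and may only label patients. The count model is to follow the same analytical framework as the logistic one. Functional form is often left to a statistical analysis plan, and that plan is not shown.

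Much of this stands. A reader might infer that all liver exposures are cut, or that the study will lose between a quarter and two thirds of its information. The documents support neither. The first goes beyond the wording of the logistic model. The second turns assumed shares into a fact of this study, and its upper end is not borne out at an odds ratio of 1.42.

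It also stands that NAFLD is a composite of ALT, weight and alcohol. Log ALT cannot replace it, and the single-variable loss formula does not apply to it. A true threshold effect would shrink or reverse the loss.

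What remains is that the only form given for fibrosis is banded, objective 2 is framed as presence, and the count-model sentence names abnormal enzymes. These are statements in the current text, not silence. Because the sections differ, the scale could also be chosen after results are seen.

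**Conclusion.** The point holds for two exposures: FIB-4, given only as three bands, and the enzymes in the adenoma-count model, described as abnormal. It does not extend to the blood markers of the logistic model or to NAFLD.

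The size is conditional. If only classes are used, the loss is at least about 36% for a two-class cut, about 42 to 57% with 20% or 10% of patients above it, and about 20 to 45% for three FIB-4 bands. This rests on a roughly normal exposure on the log scale, a smooth and roughly linear effect, and assumed shares; the two-class range also takes the odds ratio of 1.42 as per standard deviation. The two-class range was checked in logistic models only and carries over to the count model as an approximation. The change is worth making because a better method is available from data already collected.

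**What to change.** Amend section 6 as follows, for both the logistic and the count models:

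1. Test fibrosis (objective 2) with continuous log FIB-4, either linear or as a restricted cubic spline with three knots.
2. Test ALT, AST and GGT as continuous log values, and reword the count-model sentence to refer to enzyme levels.
3. Fit FIB-4 in a separate model from its components ALT and AST, and keep the age adjustment.
4. Keep the composite NAFLD definition as its own exposure.
5. Keep the FIB-4 bands and ALT limits for description and clinical reporting.

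No new data are needed. A three-knot spline for FIB-4 uses 2 degrees of freedom, the same as three bands, and a linear term uses one fewer. Each splined enzyme adds at most one degree of freedom, to be counted within the allowance of k = 15. If three splined enzymes came on top of it, k = 18 would give 10 × 18/0.15 + 10 × 18/0.35 = 1200 + 514 = 1714 patients, above 1430 but below the cap of 2000. Log-linear enzyme terms avoid that cost.
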